7.11	Public disclosure and publication policy	19
9.	TIME SCHEDULE	20
10.	REFERENCES.....	21
11.	APPENDIX	2

LIST OF ABBREVIATIONS AND RELEVANT DEFINITIONS

ABR	ABR form (General Assessment and Registration form) is the application form that is required for submission to the accredited Ethics Committee (ABR = Algemene Beoordeling en Registratie)
AE	Adverse Event
AR	Adverse Reaction
CA	Competent Authority
CCMO	Central Committee on Research Involving Human Subjects
CV	Curriculum Vitae
DSMB	Data Safety Monitoring Board
EU	European Union
EudraCT	European drug regulatory affairs Clinical Trials GCP Good Clinical Practice
IB	Investigator's Brochure
IC	Informed Consent
IMP	Investigational Medicinal Product
IMPD	Investigational Medicinal Product Dossier
METC	Medical research ethics committee (MREC); in Dutch: medisch ethische toetsing commissie (METC)
(S)AE	Serious Adverse Event
SPC	Summary of Product Characteristics (in Dutch: officiële productinformatie IB1-tekst)
Sponsor	The sponsor is the party that commissions the organisation or performance of the research, for example a pharmaceutical company, academic hospital, scientific organisation or investigator. A party that provides funding for a study but does not commission it is not regarded as the sponsor, but referred to as a subsidising party.
SUSAR	Suspected Unexpected Serious Adverse Reaction
Wbp	Personal Data Protection Act (in Dutch: Wet Bescherming Persoonsgevens)
WMO	Medical Research Involving Human Subjects Act (Wet Medisch-wetenschappelijk Onderzoek met Mensen)

SUMMARY

Rationale: Perianal fistulas are a common incapacitating problem. Many patients are treated by seton drainage to prevent recurrent abscess formation. Nowadays, vessel loops or sutures are used for drainage. The knot of these seton drains can cause complaints of pain or tenderness if it presses against the external opening of the fistula or even slides in to the fistula tract. Medishield B.V. designed a knotless seton drain, the SuperSeton. This could decrease the pain complaints caused by the knot.

Objective: With this study we aim to determine the feasibility of SuperSeton placement in patients with perianal fistulas.

Study design: The design of the study is a feasibility study.

Study population: Patients (≥ 18 years) with perianal fistulas (ever) treated with a knotted seton are eligible.

Intervention: The SuperSeton will be placed at the outpatient clinic in patients that already have a seton in situ. This seton will then be exchanged by the SuperSeton. In case patients do not have a seton in situ, the SuperSeton can be placed at the operating theatre in day care setting instead of a regular seton.

Main study parameters/endpoints: The primary outcome is seton failure (loosening of the seton). Secondary outcomes are time of procedure, complications and quality of life measured by the PDAI ('Perianal Disease Activity Index').

Nature and extent of the burden and risks associated with participation: The SuperSeton will be placed in patients with perianal fistulas (ever) treated with a conventional knotted seton. There are no additional risks involved. The seton will be placed at the outpatient clinic in patients with a seton in situ, or at the operating theatre in day care setting in patients with a perianal abscess without a seton. The material that is used for the Setons is of medical grade polyurethane, this is the same material of catheters that are already used in clinical practice (instech BTPU 027). The Setons including the insert (BTPU) are supplied sterile (Synergy Health). **Sample size calculation:** A group of 60 patients will be included to determine feasibility of the SuperSeton. The proposed treatment protocol is considered feasible if at least 70% of the SuperSetons stay in place.

PARTICIPATING CENTRES

Surgeon

Academic Medical Center

[name]

[name]

Proctos Kliniek

[name]

INTRODUCTION AND RATIONALE

1.1 Introduction & rationale

Perianal fistulising disease is associated with local pain, discharge, and considerable morbidity rates (including sphincter and perineal tissue destruction) resulting in a negative impact on quality of life.¹ The main cause of perianal fistula development is sepsis originating from the cryptoglandular glands.² Other aetiologies are Crohn's disease (CD), malignancies, radiation, trauma or foreign bodies. In simple or low fistulas (lower one-third of the external sphincter) treatment consists of lay open techniques and recurrences are hardly seen.

In contrast, complex or high perianal fistulas (upper two-third of the external sphincter) have limited treatment options. The most frequently used treatment approach has been surgical non-cutting seton placement for chronic drainage of the fistula. This technique dates back to the ancient times. A seton maintains patency of the tract and eliminates the accumulation of pus which prevents the recurrent formation of tracts and abscesses. In addition, fibrosis of the fistula tract can be achieved.

However, the seton has been reported to negatively influence quality of life and is associated with a decreased Perianal Disease Activity Index (PDAI score).³ Closure rates after seton removal vary widely in patients with CD (13.6%-100%).⁴ Nowadays, vessel loops or sutures are used as seton to drain the fistula. The ends of the seton drain are connected by a knot or a suture according to known methods. A knotted seton is relatively difficult to clean, and the knot has a tendency to rotate towards the external opening of the fistula tract and sometimes even migrate in to the fistula tract. This may cause complaints of pain and discomfort. This matter is widely discussed on patient forums. Last year, a survey regarding complaints of the knot of the seton, was send via the website of the CCUVN (Crohn en Colitis Ulcerosa Vereniging Nederland) to patients with perianal fistulas. This survey showed that complaints varied from irritation, discharge of blood and/or pus, pain and itching. Sitting and bicycling were mentioned as activities that aggravated the symptoms. Up till now one other knotless seton is available, the Comfort Drain.⁵

Recently, MediShield B.V. developed a knotless seton, the 'SuperSeton'. This seton connects the two ends of the drain to form a smooth closed loop. It is expected that this smooth joint will decrease pain and discomfort in patients with perianal fistulas that are treated by seton drainage. In addition, the SuperSeton can make placement of the seton less complex for the surgeon.

With this study we will be able to comment on the feasibility of the SuperSeton.

2. OBJECTIVES

With this study we aim to determine the feasibility of SuperSeton placement in patients with perianal fistulas.

Primary Objective:

The primary objective of this study is to determine feasibility of the SuperSeton drain.

Secondary Objectives:

Secondary outcomes are time of procedure, complications and quality of life measured by the PDAI ('Perianal Disease Activity Index').

3. STUDY DESIGN

The design of the study is a feasibility study with SuperSeton placement in patients with perianal fistulas. The trial will be conducted in the AMC and the Proctos Kliniek. Patients fulfilling the inclusion criteria without any exclusion criteria will be included in the study. The total inclusion is scheduled to take place within 10 months.

Patients will be seen at the outpatient clinic 3 months after SuperSeton placement by the surgeon. Other visits will be scheduled on indication. During these contacts the PDAI score will be assessed. Patients will be followed by the research resident to assess complications or re-admissions.

4. STUDY POPULATION

4.1 Population (base)

Patients with a perianal fistula for which a seton was already placed in day care setting (that is still in situ) and patients presenting with a recurrent perianal fistula (ever treated with a knotted seton) for which a new seton will be placed are eligible.

4.2 Inclusion criteria

- ≥ 18 years
- Written informed consent
- Perianal fistula with a seton in situ or a recurrent perianal fistula for which a new seton will be placed

4.3 Exclusion criteria

- Patients with a pacemaker or an ICD in situ
- Rectovaginal fistula
- Patients with a stoma
- Life expectancy < 2 years
- The inability of reading/understanding and filling in the questionnaires
- Dementia or altered mental status that would prohibit the understanding and giving of informed consent
- Participation in another trial

4.4 Sample size calculation

The sample size calculation is based on a clinically relevant decrease in the PDAI and number of re-interventions. The PDAI has 5 items, subdivided in a 5-point Likert scale (range 0-20). A score of >7 is considered as serious perianal disease. The CCUVN survey indicated that the PDAI reflected severe complaints in Crohn's fistula patients, with high scores on all 5 scales (average 9.2). A decrease to 6.9 is considered to be clinically relevant (<7 considered as moderate perianal complaints). In the survey it also became apparent that 50% required re-interventions related to the knot. Reducing the 50% of reinterventions to 30% is considered clinically important and can be expected due to the stronger insert connection and less knot-related complaints.

The sample size needed to demonstrate superiority of the SuperSeton with a significant decrease in PDAI and number of re-interventions is 60 patients (alpha 0.05, power 90%, and 5% drop-out).

Feasibility:

The proposed treatment protocol is considered feasible if at least 70% of the SuperSetons stay in place.

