5. TREATMENT OF SUBJECTS

5.1 Investigational product/treatment

Patients with an established perianal fistula and a seton in situ or for which a new seton will be placed will be included in the study.

All patients start with the placement of the SuperSeton at the outpatient clinic or at the operating theatre in day care setting. The flow chart is demonstrated in the attached figure 1 (Appendix). After 3 months, the feasibility of the SuperSeton will be assessed.

The SuperSeton is made of medical grade Polyurethaan, which is widely already used in clinical practice as catheters (instech BTPU 027). The setons including the insert (BTPU) are delivered sterile (Synergy Health). Therefore, there is no additional risk associated with SuperSeton placement.

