6. METHODS

6.1 Study parameters/endpoints

6.1.1 Main study parameter/endpoint

- The primary outcome is seton failure (loosening of the seton)

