6.2 Study procedures

Informed consent will be obtained at the outpatient department in all eligible patients by the study team. Seton replacement will be performed at the outpatient clinic and new setons will be placed at the operating theatre in day care setting. All patients will be followed for 3 months by the study team. The flow chart is provided in the attached figure 1 (Appendix).

Patients will be contacted by telephone after \pm 3 months the study coordinator to assess complications, additional interventions, re-admissions, duration of hospital stay and visits to the outpatient clinic.

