6.9 Statistics

All data will be collected in an electronic database by the AMC study coordinator. The outcome parameters will be analysed after 3 months follow up with appropriate statistical tests using the statistical program SPSS. A two-tailed $p < 0.05$ is considered statistically significant. Descriptive statistics will be used to describe patient characteristics and outcomes. Preoperative PDAI scores will be compared to postoperative PDAI scores after 3 months follow up. Results will be analysed using the paired t -test.

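### Section 4.4 claims powered superiority on re-interventions, but the trial has one arm, no outcome list names re-intervention, and the only comparator is a survey rate with no stated period

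*Protocol*

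**What the plan says.** Section 4.4 rests the sample size on two effects, a fall in PDAI from 9.2 to 6.9 and a fall in re-interventions from 50% to 30%. It concludes: "The sample size needed to demonstrate superiority of the SuperSeton with a significant decrease in PDAI and number of re-interventions is 60 patients" (alpha 0.05, 90% power, 5% drop-out). The 50% is sourced as follows: "In the survey it also became apparent that 50% required re-interventions related to the knot". Section 1.1 describes that survey as one about complaints of the knot, sent out the previous year through the website of a Crohn's and colitis patient association.

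The rest of the protocol describes a different kind of study:

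- Section 3 calls it a feasibility study, and section 5.1 says: "All patients start with the placement of the SuperSeton at the outpatient clinic or at the operating theatre in day care setting".
- The primary outcome in section 6.1.1 is loosening of the seton.
- Section 2 says: "Secondary outcomes are time of procedure, complications and quality of life measured by the PDAI". The summary and section 6.1.2 give the same list.
- Interventions appear only in section 6.2, as one item of a telephone call at about 3 months: "to assess complications, additional interventions, re-admissions, duration of hospital stay and visits to the outpatient clinic".
- The one comparison that section 6.9 names is for PDAI: "Preoperative PDAI scores will be compared to postoperative PDAI scores after 3 months follow up".
- The summary justifies the same 60 patients by feasibility alone.

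**The concern.** A superiority claim needs a comparator. PDAI has one, each patient's own baseline. Re-intervention has none inside the trial, so the survey's 50% must serve, and it does not match what the trial will observe in three respects.

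- **Period.** The protocol does not say over what time the 50% accrued, nor how many people answered. The trial observes about 3 months.
- **Event.** The survey figure counts re-interventions related to the knot. The SuperSeton has no knot ("This seton connects the two ends of the drain to form a smooth closed loop"), while the 3-month call collects any additional intervention.
- **Population.** The survey went out through a Crohn's and colitis association, so a mainly Crohn's sample is likely, although this is not stated for the 50%. Eligibility in section 4.2 is not limited to Crohn's disease.

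A 3-month proportion below 50% could therefore reflect the period, the event definition or the patients instead of the device, and a real benefit could be hidden in the same way. A reader or ethics committee relying on section 4.4 would expect a powered device comparison that the trial cannot give, on an outcome it does not list.

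**Working it through.** **Inputs.** From section 4.4: comparator 0.50, target 0.30, alpha 0.05, power 0.90, drop-out 5%, N = 60. From section 6.9: two-sided testing. Evaluable patients: 60 × 0.95 = 57.

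**1. Reproducing the 60.** For one sample against a fixed 0.50, with the variance taken at 0.30:

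n = (1.960 + 1.282)² × 0.30 × 0.70 / (0.50 − 0.30)² = 55.2, so 56; 56/0.95 = 58.9, so 59.

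This is close to 60. With the null variance in the alpha term:

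n = (1.960 × √0.25 + 1.282 × √0.21)² / 0.04 = 61.4, so 62; 62/0.95 = 65.3, so 66.

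A concurrent 1:1 knotted-seton arm would need 124 per arm, 248 in all, or 262 after drop-out. Sixty patients split 30/30 would have about 35% power. So the 60 fits only a one-sample test in which the survey rate is treated as known without error. The PDAI half of the claim cannot be checked, because no standard deviation is given.

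**2. Power at 57 evaluable.** The exact binomial test against 0.50, with at most 0.025 in the lower tail, rejects at X ≤ 20 (lower tail 0.0166). P(X ≤ 20 | n = 57, p = 0.30) = 0.837. The smallest n whose exact power reaches 0.90 is 65 evaluable (X ≤ 24, power 0.910).

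**3. What a mismatched comparator does.** Assume the device has no effect, and that the true 3-month rate for knotted setons in this population is p, where the documents give no value. The chance of declaring superiority to 50% is P(X ≤ 20 | n = 57, p):

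| Assumed true 3-month rate p | Probability of declaring superiority |
|---|---|
| 0.50 | 0.017 |
| 0.45 | 0.084 |
| 0.40 | 0.269 |
| 0.35 | 0.566 |

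In the other direction, if the true knotted rate were 0.60 and the device cut it to 0.40, the same test would detect this with probability 0.269.

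**4. The period alone.** Assume a constant hazard, no device effect, and that the 50% accrued over T months. The 3-month rate is 1 − 0.5^(3/T).

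| Assumed T (months) | 3-month rate | Probability of declaring superiority |
|---|---|---|
| 3 | 0.50 | 0.017 |
| 6 | 0.29 | 0.87 |
| 12 | 0.16 | above 0.999 |

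The protocol does not say which of these cases applies.

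**5. Precision of 60 patients (Clopper-Pearson 95%).** Setons in place: 42/60 = 70%, interval 56.8% to 81.2%; 40/57 = 70%, interval 56.6% to 81.6%. Re-interventions: 18/60 = 30%, interval 18.8% to 43.2%.

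**The case against.** **The power shortfall depends on the test.** Section 6.9 does not name an exact test. A normal-approximation test rejects at X ≤ 21 of 57 and has 89.7% power at a true rate of 30%; with all 60 evaluable it rejects at X ≤ 22 and has 89.6%. This stands as arithmetic, and a difference between 59 and 60 is ordinary rounding. But the attained two-sided size is then 0.063 at 57 (2 × 0.0314) and 0.052 at 60, so the stated alpha and power are not delivered together. The shortfall is in any case the lesser part of the point.

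**The events may be closer than they look.** Section 4.4 attributes the expected fall partly to a stronger insert connection, whose failure would be loosening, the primary outcome; and 30% is the complement of the 70% feasibility threshold. That link is an inference the protocol does not state, and it supplies neither a control nor a matching period.

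**An analysis plan may exist.** The absence of a named test for re-interventions is rightly given little weight. A later plan cannot, however, add a control group to the design fixed here.

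**The simulated test is not planned.** This is true, and the assumed rates and periods come from no document. They show what the superiority claim would mean if acted on; the conclusion does not rest on them.

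**It is only a feasibility study.** No objective claims superiority and the primary outcome is untouched. This limits the severity, but it is also the reason the superiority wording does not belong in section 4.4.

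**Conclusion.** The concern holds. Section 4.4 attributes to the trial a superiority conclusion on re-interventions, with 90% power, that a single-arm study with no listed re-intervention outcome and a non-comparable survey benchmark cannot deliver. This rests on the protocol's own text and needs no outside assumption.

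The size of the effect is conditional. Power is about 84% at 57 evaluable patients under an exact two-sided 0.05 test, and close to 90% only under an approximation that exceeds the stated alpha. The chance of wrongly declaring superiority runs from 1.7% to 57% over assumed true 3-month rates of 50% down to 35%, and higher still if the survey's 50% accrued over 6 months or more at a constant hazard.

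This should be fixed, but it does not endanger the trial: the primary outcome, the 70% rule and the paired PDAI comparison stand.

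**What to change.** - **Section 4.4.** Remove the superiority claim and the 90% power statement for re-interventions, and keep the survey's 50% as background only. Support the 60 by the precision of the primary outcome, in line with the summary. Suggested wording: *If the SuperSeton is in place at 3 months in 42 of 60 patients (70%), the exact 95% CI is 57% to 81%; with 40 of 57 evaluable it is 57% to 82%.*
- **Sections 2 and 6.1.2.** Name seton-related re-intervention within 3 months as a descriptive secondary outcome, reported with an exact 95% CI (for example 18 of 60: 30%, 19% to 43%) and no test against the survey.
- **Section 6.2.** Record at the existing 3-month call whether each additional intervention was seton-related.
- **Section 6.9.** Keep the paired PDAI comparison, described as a within-patient before-after change.

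The cost is a wording amendment and one data field, with no extra patients or visits. The downside is that the superiority claim on re-interventions is given up, and the modest precision of the feasibility estimate becomes visible: a lower limit of 57% at an observed 70%.

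### Section 4.4 claims that 60 patients can demonstrate superiority of the SuperSeton, but the study has one arm and only survey reference values; the stated 90% power for re-interventions is also somewhat optimistic at a two-tailed 5% level

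*Protocol*

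**What the plan says.** Section 4.4 of the Protocol gives the basis for the sample size: "The sample size needed to demonstrate superiority of the SuperSeton with a significant decrease in PDAI and number of re-interventions is 60 patients", with the settings "alpha 0.05, power 90%, and 5% drop-out". The re-intervention reference comes from a patient survey: "In the survey it also became apparent that 50% required re-interventions related to the knot". The target follows: "Reducing the 50% of reinterventions to 30% is considered clinically important". For PDAI, the same survey gave a mean of 9.2 in Crohn's fistula patients, and 6.9 is the target.

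The design has a single group. Section 3 states: "The design of the study is a feasibility study with SuperSeton placement in patients with perianal fistulas". Section 5.1 adds: "All patients start with the placement of the SuperSeton at the outpatient clinic or at the operating theatre in day care setting". Section 6.9 sets the significance level: "A two-tailed $p < 0.05$ is considered statistically significant". The only test it names is a paired t-test of PDAI before placement and at 3 months.

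The Summary gives the same number another purpose: "A group of 60 patients will be included to determine feasibility of the SuperSeton". It cites only the 70% rule, which section 4.4 puts under a separate feasibility heading.

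**The concern.** Superiority is a statement about one treatment relative to another. Here the other treatment, the knotted seton, is not given to any study group, and its results are represented by two survey averages. A significant result could then be reported as proven superiority because the protocol said that the study was sized to prove it.

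The second question is whether 60 patients deliver the stated 90% power for re-interventions. If they do not, a non-significant result would be given more weight as negative evidence than it deserves.

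Finally, a reader who compares the Summary with section 4.4 cannot tell which question the 60 was calculated for.

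**Working it through.** **Superiority.**

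- Re-interventions: the observable quantity is one proportion in SuperSeton patients. The 50% is a survey figure, treated as fixed. Rejecting 50% shows a rate below that figure. It does not separate the device from differences between survey respondents and trial patients, or from differences in follow-up and in how re-interventions are counted.
- PDAI: the planned analysis compares each patient with his or her own baseline. A fall shows change over 3 months, not an advantage over a knotted seton followed for the same 3 months. Section 4.2 also admits patients with a recurrent fistula who receive a new seton. Their baseline need not be a knotted-seton state.
- Population: the survey mean of 9.2 is for Crohn's fistula patients, while section 4.2 does not limit entry to Crohn's disease.

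**Power for re-interventions.** Inputs: reference 0.50, target 0.30, alpha 0.05, power 90%, drop-out 5% (all section 4.4), and two-tailed testing (section 6.9). Evaluable patients: 60 × 0.95 = 57.

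1. *Reproducing the 60.* One-sample normal approximation with the variance at 30%: n = (1.96 + 1.2816)² × 0.30 × 0.70 / 0.20² = 55.2, so 56 evaluable. 56 / 0.95 = 58.9, so 59 enrolled, in line with the stated 60. Nominal power at 57 by this formula is 90.9%.
2. *Score formula* (variance at 50% under the null, 30% under the alternative): n = (1.96 × 0.5 + 1.2816 × √0.21)² / 0.04 = 61.4, so 62 evaluable and 66 enrolled. Power at 57: Φ[(0.2 × √57 − 1.96 × 0.5) / √0.21] = Φ(1.157) = 87.6%.
3. *Power of actual tests at 57*, from binomial sums:

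| Test (two-sided 5%) | Rejects at | True alpha | Power at 30% |
|---|---|---|---|
| Exact binomial, or continuity-corrected z | ≤ 20 | 3.3% | 83.7% |
| Uncorrected z, or mid-p | ≤ 21 | 6.3% | 89.7% |

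With all 60 evaluable, the exact test has 83.8% (true alpha 2.7%) and the uncorrected z-test 89.6% (true alpha 5.2%).

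4. *One-sided 5% level.* Exact power is 91.3% at 56, 89.7% at 57, 92.6% at 58, 91.2% at 59 and 93.7% at 60. At 57, the uncorrected z-test has 93.8% and the score formula gives 93.3%.

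**PDAI.** The planned difference is 9.2 − 6.9 = 2.3. Section 4.4 gives no standard deviation, so this half cannot be reproduced. As an assumed range for the SD of change with 57 patients and a paired t-test: SD 4 gives 98.9%, SD 5 gives 92.7% and SD 6 gives 81.2%.

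**The case against.** The objectives in section 2 claim only feasibility, so the superiority phrase could be called loose wording in one sentence. That limits its reach, but the phrase stands in the justification of the sample size and says what the 60 patients are for. Section 7.6 refers to randomised patients, from which a reader might infer a second arm. No other section describes allocation or a comparator, and section 5.1 excludes it.

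On power, the objections are substantial:

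- A reader might infer that the 60 is an arithmetic error. It is not: a standard planning formula gives 59.
- A reader might infer that 90% fails on any reading. It does not: section 4.4 does not state sidedness, and a one-sided 5% level gives essentially 90%. The shortfall depends on applying the two-tailed level of section 6.9.
- No test of re-interventions is named. Part of the exact test's shortfall is unused alpha (3.3% of the 5%), and one more evaluable patient raises its power to 87.9%. The uncorrected z-test misses 90% by only 0.3 points, though with true alpha above 5%.
- A within-patient paired test could exceed 90%, but only if the share of discordant patients is below about 0.24. Section 4.4 neither describes such a test nor gives that share.
- Re-interventions are not among the endpoints in section 6.1, and the feasibility decision rests on the 70% rule. The consequence is therefore limited.

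The two statements about the 60 do not conflict numerically. The Summary may simply be compressed, so that point is minor.

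**Conclusion.** The superiority claim does not hold for this design. It needs no modelling assumption: there is one arm, and the reference values come from a survey. The attainable conclusions are a re-intervention rate below the survey value and a change in PDAI from baseline.

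The power statement is optimistic rather than wrong. At 57 evaluable patients and a two-tailed 5% level, it is 83.7% (exact, 6.3 points below 90%), 87.6% (score formula, 2.4 points below) or 89.7% (uncorrected z, 0.3 points below, true alpha 6.3%). This assumes a true rate of 30%, the survey 50% treated as known without error, and section 6.9 governing sidedness.

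Nothing here shows that the study is too small for its feasibility question, and the 70% rule is unaffected.

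**What to change.** Keep 60 patients and reword:

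1. In section 4.4, replace the superiority claim with a comparison of the re-intervention rate against the survey reference value, and of PDAI against each patient's baseline.
2. State re-intervention power at 57 evaluable patients as about 84-90% two-sided, depending on the test, or as about 84% if an exact test is intended.
3. Let the Summary refer to the section 4.4 calculation, and name the 70% rule there as the separate feasibility criterion.

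The cost is a protocol text change. The stated power and the possible conclusion become more modest. No patients, visits or procedures are added.

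### Section 4.4 justifies 60 patients by 90% power for superiority on PDAI and re-interventions, but the primary question is seton retention and there is no control group

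*Protocol*

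**What the plan says.** Section 4.4 bases the sample size on two quantities: a fall in mean PDAI from 9.2 to 6.9, and a fall in re-interventions from 50% to 30%. It concludes: "The sample size needed to demonstrate superiority of the SuperSeton with a significant decrease in PDAI and number of re-interventions is 60 patients". The settings follow in the same sentence: "number of re-interventions is 60 patients (alpha 0.05, power 90%, and 5% drop-out". The 50% comes from a patient survey: "In the survey it also became apparent that 50% required re-interventions related to the knot".

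Under a separate feasibility label, the same section gives the decision rule: "The proposed treatment protocol is considered feasible if at least 70% of the SuperSetons stay in place". No error rate, target rate or precision is attached to that rule.

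Elsewhere the protocol puts the question differently:

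- Section 2: "The primary objective of this study is to determine feasibility of the SuperSeton drain".
- Section 6.1.1 names seton failure, meaning loosening, as the primary outcome.
- Section 6.1.2 lists PDAI as secondary. Re-intervention appears in neither endpoint list. Section 6.2 only has additional interventions collected at the telephone contact at about 3 months.
- The Summary gives another reason for the same number: "A group of 60 patients will be included to determine feasibility of the SuperSeton".
- Section 5.1 has all patients start with a SuperSeton. No comparison group is described.
- Section 6.9 names one comparison, PDAI before placement against PDAI at 3 months, by paired t-test at a two-tailed 5% level.

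**The concern.** The only power statement in the protocol belongs to outcomes that do not decide the trial. A reader of section 4.4 takes away 90% power for superiority, while the conclusion will rest on a retention proportion for which the protocol does not say what 60 patients can deliver.

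The word superiority adds a second problem. It invites a conclusion about the SuperSeton against knotted setons. A single group compared with its own baseline, or with a survey percentage, cannot support that conclusion.

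**Working it through.** **1. Reproducing the 60 from the re-intervention rates.** Inputs from section 4.4: 50% reference, 30% target, alpha 0.05, power 90%, drop-out 5%. Section 4.4 does not state sidedness, so two-sided is taken from section 6.9. One-sample normal approximation against a fixed 50%, with variance at 30%:

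n = (1.960 + 1.2816)² × 0.30 × 0.70 / 0.20² = 10.508 × 0.21 / 0.04 = 55.2, so 56 evaluable.

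With drop-out: 56 / 0.95 = 58.9, so 59 enrolled, against 60 in the protocol. The figure is roughly reproduced.

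Other two-sided one-sample methods give more after drop-out: score 66, arcsine 67, null variance 70, continuity-corrected 71, exact binomial 74. Evaluable patients from 60 enrolled: 60 × 0.95 = 57. The exact two-sided test at n = 57 rejects on the low side at 20 or fewer re-interventions, and P(X ≤ 20 | n = 57, p = 0.30) = 83.7%. At n = 60 the cut-off is 21 and the power 83.8%. So 90% is somewhat optimistic if an exact test is used.

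**2. The PDAI part.** The difference is 9.2 − 6.9 = 2.3. No standard deviation is given, so the power cannot be checked. For 90% power with 57 evaluable patients, the SD of the change would have to be about 2.3 × √57 / 3.2416 = 5.4. Over an assumed range of SDs, a paired t-test at n = 57 has power 99% (SD 4), 93% (SD 5), 81% (SD 6) and 57% (SD 8).

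**3. What 60 patients give for the primary outcome.** Assumption: one SuperSeton counted per patient. The rule then needs 0.70 × 60 = 42 in place, or 0.70 × 57 = 39.9, so 40 of 57.

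Exact (Clopper-Pearson) 95% intervals:

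- 42/60: 56.8% to 81.2%
- 40/57: 56.6% to 81.6%

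Probability that the rule is met, from the binomial distribution (the true rates are assumed values):

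| True retention | P(X ≥ 42), n = 60 | P(X ≥ 40), n = 57 |
|---|---|---|
| 60% | 7% | 7% |
| 65% | 25% | 25% |
| 70% | 56% | 55% |
| 75% | 85% | 84% |
| 80% | 98% | 97% |

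**4. What superiority could mean here.** For PDAI, the paired test asks whether scores change from baseline. One group can answer that, but regression to the mean and natural course remain as explanations besides the device. For re-interventions, the only reference is the survey's 50%, for which no time window is given. Section 1.1 says the survey went out through a Crohn's and colitis patient association. Eligibility is not limited by cause ("Perianal fistula with a seton in situ or a recurrent perianal fistula for which a new seton will be placed"), and section 1.1 names another leading cause: "The main cause of perianal fistula development is sepsis originating from the cryptoglandular glands". The survey and trial populations may therefore differ.

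**The case against.** The strongest replies are these.

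- **Section 4.4 is open about its basis.** It says at the outset that it uses PDAI and re-interventions, and it sets the retention rule apart. Sizing on a secondary outcome is not in itself an error, and a descriptive threshold is common in a feasibility study. This stands, and it limits the point to justification and wording.
- **A single group can test PDAI change.** This also stands. A reader might infer that nothing in section 4.4 is testable without a control arm, or that PDAI is compared with the survey. Section 6.9 does not support that: the comparison is within patients, and the survey's 9.2 serves as a planning value. The criticism of the survey as reference applies to re-interventions only.
- **The two rates may be linked.** The 30% re-intervention target is the complement of 70% in place, and section 4.4 partly credits the expected fall to a stronger connection. The protocol does not state the link, and fewer knot complaints are credited as well. Even on that reading the calculation tests against 50%, whereas the rule asks for 70% observed, which is met with probability 56% when true retention is 70%.
- **There may be a control arm.** Section 7.6 speaks of randomised patients, and the flow chart is not shown. No allocation or comparator is described in the Summary, section 3 or section 5.1, so the phrase looks like a stray.

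Two further inferences are tempting. One is that the sample size is miscalculated, but one standard approximation reproduces it to within one patient. The other is that the survey's 50% overstates the 3-month rate, so that 30% would show no benefit. With no survey window given, the documents do not allow that to be quantified.

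**Conclusion.** The point holds as a defect of justification and wording that should be fixed. The stated 90% belongs to PDAI and re-interventions and says nothing about retention, which decides the trial. For retention, 60 patients give an interval of about 12 to 13 percentage points either side of 70%. The rule would call a device with true retention of 65% feasible about one time in four. These figures assume one SuperSeton per patient and independent patients.

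Superiority over knotted setons is not something this design can show. Change in PDAI from baseline can be tested, but its power cannot be verified without an SD. A reader might go further and infer that 60 patients are too few or that a control arm is required. The documents do not support that: the declared aim is feasibility, and no required precision is stated against which 60 falls short.

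**What to change.** Keep 60 patients.

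1. Add a precision statement for the primary outcome to section 4.4 and the Summary, worded as what 60 patients deliver and not as how the number was derived. For example: 'Counting one SuperSeton per patient, at 42/60 (70%) the exact 95% CI is about 57% to 81% (40/57: 57% to 82%). The rule of at least 70% in place is met at n = 60 with probability 7%, 25%, 56%, 85% and 98% if true retention is 60%, 65%, 70%, 75% and 80%.'
2. In section 4.4, replace the aim of demonstrating superiority by estimating the change in PDAI from baseline and the 3-month re-intervention rate.
3. Either relabel the 90% figure as an approximate secondary planning calculation for re-interventions against a fixed survey rate of 50%, and list re-intervention in section 6.1.2, or delete the figure.

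The cost is a wording amendment to section 4.4 and the Summary, plus one line in section 6.1.2 if re-intervention is kept. Patient numbers, conduct and follow-up do not change. The downside is that the superiority and 90% power claims are lost and the wide retention interval becomes visible.
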